#### 9.2 Selection of Subject Population

The selection criteria have been chosen to identify a suitable population of subjects to investigate the study objectives and to minimize safety concerns in this population.

# 9.2.1 Inclusion Criteria

To be eligible for study participation, the treating investigator will ensure each subject meets all study inclusion criteria at the screening (Scr) and/or baseline (BL) visit as follows:

[figure not shown]
Inclusion criteria	Scr	BL
1. Healthy female aged 35 to 65 years at the time of screening.	X	
2. Moderate to severe fine lines, wrinkles, laxity, and crepiness of the décollete that is amenable to improvement with non-invasive intervention and is not severe enough for surgical intervention.	X	
TCC		

## 9.2.2 Exclusion Criteria

Subjects meeting any of the following criteria at the screening (Scr) and/or baseline (BL) visit are not eligible to participate in the study:

Exclusion criteria	Scr	BL
Presence of an active systemic or local skin disease that may affect wound healing.	X	X
Scarring in area(s) to be treated.	X	X
CCI	C	
Active implants (e.g., pacemakers or defibrillators), ports, or metallic implants in area(s) to be treated.	X	X
Breast implants or is planning to receive breast implants during the study.	X	X

Exclusion criteria	Scr	BL
CCI		
Inability to take pre-treatment medications due to a pre-existing condition, medication allergy, or medical issue that, at the discretion of the treating investigator, is contraindicated.	X	X
CCI		

## 9.2.4 Subject Enrollment

Subjects are considered to be enrolled when they provide informed consent (i.e., sign the ICF), meet all eligibility criteria, or are treated.

Screen failures are defined in Section 9.2.5.

#### 9.2.5 Screen Failures

Subjects who provide informed consent but who do not meet eligibility criteria or who withdraw consent prior to being treated at the baseline visit will be defined as screen failures. The investigator will maintain all source documentation for all subjects who are considered screen failures. Minimal information will be collected in the electronic data capture (EDC) system for screen failures, such as date of informed consent, demographics, and reason for screen failure. In cases when a subject is not meeting eligibility criteria due

to a temporary condition, this subject may be rescreened, at the discretion of the treating investigator, upon resolution of the temporary condition.

### 9.2.6 Removal of Subjects from Therapy or Assessment

#### 9.2.6.1 Treatment Discontinuation

If study treatment is discontinued during administration, the investigator will record the reason for treatment discontinuation in the study records. Potential reasons for discontinuation of treatment may include refusal by the subject to receive additional treatment or physician's decision. The investigator should request that a subject discontinuing treatment continue to participate in the study and complete all remaining visits and safety follow-up assessments. For subjects declining continued study participation after treatment discontinuation, additional information regarding subject withdrawal is provided in Section 9.2.6.2.

If the subject experiences escalating pain during the Ultherapy procedure that is not adequately controlled with the initially selected treatment regimen, the investigators may use their discretion to utilize further protocol-specific options to control pain (Section 10.5.1.2). Attempts should be made to optimize pain medication so that treatment can be completed.

#### 9.2.6.2 Subject Withdrawal or Discontinuation

Each subject will be followed to the end of study, or until the sponsor decides to terminate the study, whichever comes first. The only reasons a subject will not be followed for all scheduled visits include withdrawal of consent, continuous non-compliance with protocol requirements, or loss to follow-up (e.g., moving away from study site; unresponsive to attempts to contact the subject). Additionally, the investigator can discontinue any subject, at any time, if medically necessary.

Subjects have the right to withdraw from the study at any time at their own request without prejudice. In cases of withdrawn consent, data collected until the date consent was withdrawn will be analyzed as recorded.

If a subject does not attend a required study visit, the following actions will be taken:

- The site will attempt to contact the subject at least twice and reschedule the missed visit as soon as possible. Every effort to regain contact with the subject will be made (e.g., telephone contact on different dates/times, registered mail). All contact attempts will be documented.
- If attempts to contact the subject are not successful, the subject will be considered lost to follow-up and discontinued from the study.

The reason for the subject's discontinuation should be documented in the electronic case report form (eCRF). The investigator should make every attempt to complete the recommended follow-up assessments specified for the End of Study/Early Termination visit specified in the Schedule of Events (Section 11.1), while fully respecting the subject's rights.

In the case of a reported nerve effect leading to paresthesia or weakness, as well as any severe unanticipated AE that is determined to be an AE related to the device treatment, a root-cause investigation will be conducted to determine the cause, the outcome of the event, and status of subject. The investigator and the sponsor will conduct a thorough evaluation of the event. The sponsor will then immediately make a determination if the study should be suspended (Section 9.2.8).

If a non-serious AE is unresolved at the time of the subject's final study visit, an effort will be made to follow the subject until the AE is resolved or stabilized, the subject is lost to follow-up, or some other resolution of the event occurs. The investigator should make every attempt to follow all serious adverse events (SAEs) and unanticipated adverse device effects (UADEs) to resolution. Information on pregnancy and the outcome for any subject who becomes pregnant during the study will be collected.

## 9.2.6.3 Provision of Care for Subjects after Study Discontinuation

The investigator is responsible for ensuring the adequate and safe medical care of subjects during the study. After the end of the study or after subject discontinuation, the sponsor will follow all applicable local or international regulations and guidelines with regard to follow-up care for subjects. The investigator will ensure that appropriate consideration is given to a subject's post-study care.

### 9.2.7 Suspension or Premature Termination of a Study Site

Study participation by individual sites may be suspended or prematurely terminated by the sponsor. Reasons for the suspension or premature termination of study sites include, but are not limited to, the following:

- Investigator request;
- Serious or persistent noncompliance with the protocol, local regulations, and/or GCP;
- Suspicion of fraud;
- Failure to accrue subjects at an acceptable rate; and/or
- Ethical issues.

The sponsor will provide the investigational site with written notification documenting the reason for suspension or premature termination. The sponsor will inform the responsible

regulatory authority, as appropriate, and ensure the IEC/IRB is notified. If the suspension or premature termination was in the interest of safety, the sponsor will inform all other principal investigators.

In cases of temporary suspension at an investigational site, the sponsor will conduct an analysis of the reason(s) for suspension. After completing this analysis and implementing necessary corrective actions, a temporary site suspension may be lifted. The sponsor will inform the principal investigators, the IEC/IRB, and, where appropriate, the regulatory authority of the rationale, providing relevant data supporting this decision. Concurrence must be obtained from the IEC/IRB and, where appropriate, regulatory authorities before the investigational site resumes trial activities. If subjects were informed of the suspension, the principal investigator or authorized designee will inform them of the reasons for resumption.

In cases of premature termination, the investigator will conduct site-closure activities in accordance with all applicable sponsor, local, and international guidelines and regulations.

In the event of a pandemic disease outbreak (e.g., new COVID-19 public health emergency), it may not be feasible for an investigational site to continue study participation. In this scenario, consideration will be given to the impact of investigative-site closure on the safety and well-being of participating subjects.

# 9.2.8 Suspension or Premature Termination of the Study

Should the investigator, sponsor, the FDA, or local regulatory authorities become aware of conditions arising during the conduct of this study that may warrant cessation of the study, such action may be taken. Prior to such action, consultation between the sponsor, the investigator, and, as appropriate, the FDA and/or local regulatory authorities will occur.

Reasons for suspension or premature termination of the study include, but are not limited to:

- Determination of a potential safety risk to subjects;
- Inadequate subject enrollment;
- Decision by the IEC/IRB to suspend or terminate approval/favorable opinion for the study; and/or
- Sponsor decision.

If suspicion of an unacceptable risk to subjects arises during the trial or if instructed by the IEC/IRB or regulatory authorities, the sponsor will suspend the trial while the risk is assessed. If the analysis determines that implementing necessary corrective actions is sufficient, a temporary trial suspension may be lifted. If an unacceptable risk is confirmed, the sponsor will terminate the trial.

In the event of study suspension or premature termination, the sponsor will inform all investigators and relevant regulatory authorities promptly of the study suspension/termination and reason for the action, as detailed in Section 9.2.7. The investigator will conduct site-closure activities in accordance with all applicable sponsor, local, and international guidelines and regulations.

## 9.2.9 Subject Completion

Subjects are considered to have completed the study if they receive full treatment and complete all visits defined in the Schedule of Events (Section 11.1).

# **9.2.10 End of Study**

The end of the study is defined as when the last subject completes the last visit and the database is closed.

#### 10 STUDY DEVICE AND TREATMENT OF SUBJECTS

#### 10.1 Description of Study Device

The Octave System is the second-generation Ulthera platform technology. The new Octave System is to be marketed for the same intended use and indications for use as the cleared DeepSEE system (Ulthera System K180623; originally launched in the US in 2009), namely for non-invasive dermatological aesthetic treatment to improve lines and wrinkles of the décolleté.

The Octave System consists of four primary components (console, handpiece, transducers, and cart) that allow the user to visualize and precisely deliver therapeutic heat to select tissue layers within the skin using microfocused ultrasound.

A variety of transducer designs is available at different frequencies and nominal treatment depths

Reference the current IFU for additional information related to the Octave System's technological characteristics.

## 10.1.1 Mechanism of Action

## 10.1.2 Operating Information

the user interface displayed during treatment is dominated in the center by the ultrasound image. Other control and information panels surrounding the ultrasound image enable changes in the energy level, monitor line delivery, track the treatment depth, and allow the activation of imaging and storing of ultrasound images.

When a treatment zone is selected using therapy controls on the touch panel, the energy, spacing, and length parameters will be preset to study-specific values. The maximum number of TCPs and spacing are fixed and dependent on the specific transducer inserted into the handpiece. For this clinical trial, the treating investigator will not be able to adjust the energy level – that is, all study subjects must be treated with two transducers at energy level 4

and one transducer at energy level 3

with no reduction in energy level permitted according to the study protocol.

#### 10.2 Instructions for Use and Administration

The investigational device should be used in the décolleté region in accordance with the information presented in Section 10.3. Additional information on product usage is provided in the current version of the Octave System IFU

It is recommended that the following areas be avoided during treatment with the Octave System:

- Thyroid gland, thyroid cartilage, and trachea;
- Major vessels;
- Breast tissue.

The Octave System should only be used by those trained and qualified to operate. For this clinical trial, such training will be provided by the sponsor before the start of the study. Additionally, should study personnel change during the trial, the sponsor will retrain, as necessary.

# 10.3 Methods of Assigning Subjects to Treatment Groups

Subjects who provide informed consent, complete all screening assessments, meet all eligibility criteria, and are accepted for enrollment into the study will be assigned a unique subject identification number.

Each subject will receive a unique subject number upon entry in the EDC system. In cases when subjects are not eligible for enrollment at the baseline visit (e.g., due to a temporary condition), they will be considered a screen failure. Rescreening of such a subject is allowed upon resolution of the temporary condition. In this case, a new screening number will be assigned, and all screening assessments will be repeated.

All subjects will receive a single Ultherapy treatment on the Octave System – that is, no randomization will be used.

## 10.4 Blinding Procedures

In this non-comparative study, investigators and subjects will not be blinded to treatment. Three independent, photographic evaluators will be blinded for the primary effectiveness endpoint as described in Section 8.1.

## 10.5 Study Treatment

All protocol-specific criteria for the administration of study treatment must be met and documented prior to the start of any study treatment. All treatments with the investigational device will be performed on site by the treating investigator or by delegated and qualified study personnel. Subjects will not be dispensed any investigational material. Any noncompliant subject or site may be discontinued from the study (Section 9.2.6.2 and Section 9.2.7, respectively).

#### 10.5.1 Planned Treatment Procedure and Administration

Subjects will be enrolled to receive treatment of the décolleté with two transducers at energy level 4

[figure not shown]
and one transducer at energy level 3

No reduction in energy level is permitted under this study protocol.

#### 10.5.1.1 Pre-Treatment Assessments

All subject-related, pre-treatment study activities (Section 11.1) should be completed prior to administration of pre-treatment medications.

#### 10.5.1.2 Pre-Treatment Medications and Procedure

## 10.5.1.3 Treatment Region and Administration Procedure

The general anatomic boundaries of the décolleté treatment region are delineated superiorly by the sternoclavicular notch, laterally by the midclavicular line, and inferiorly by the superior point of the intermanmary cleft. Although variations in the anatomy of medial breast tissue may occur, all investigators will be trained to avoid treating in an area overlying or including breast tissue.

[figure not shown]
To ensure appropriate collection of pain data the full line count with each transducer before moving to the next region.

Laterality is the subject's right or left.

For this clinical trial, the treating investigator will not be allowed to adjust the energy level—that is, all study subjects must be treated at the pre-defined energy level—with **no reduction in energy level permitted** according to the study protocol. Additionally, study subjects administered line counts that differ by  $\pm$  10% of the treatment guideline will be categorized as receiving a full treatment and will not be considered protocol deviations.

Investigators will be trained by the sponsor to use Octave System ultrasound imaging to ensure proper treatment is delivered (e.g., contact, depth).

## 10.5.2 Selection and Timing of Treatment for Each Subject

At the baseline visit, all enrolled healthy, adult subjects with moderate to severe fine lines, wrinkles, laxity, and crepiness of the décolleté will receive a single Octave-Ultherapy treatment of the décolleté tissue according to the treatment guidelines presented in Section 10.5.1.3. No additional treatments will be offered under this study protocol.

## 10.5.3 Treatment Interruption and Modification

If any problems occur during system operation, the treating investigator should take the following immediate action(s): lift the transducer off the subject's skin, press the **Imaging/Ready** button on the handpiece or console to discontinue treatment in progress, and/or press the red emergency **Stop** button to completely halt console operation.

As described in Section 10.5.1.2, should the subject experience escalating pain during the Ultherapy procedure that is not adequately controlled with the previously selected treatment regimen, the investigators may use their discretion to utilize further protocol-specific options to control pain. If the pain experienced by the subject remains intolerable after having administered the maximum allowable limit and type of treatment medications, treatment should be discontinued, and the subject will be followed for safety only.

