Risks of Ultherapy on the second-generation Octave System will be minimized or reduced by training the investigational sites and monitoring the subject during the treatment procedure, with careful observation of the subject's pain and skin response to treatment. Previous clinical studies with the Ulthera DeepSEE System have shown the sensory response was tolerable from both the subject's and investigator's perspective.[10] Discomfort was transient, and acute pain resolved within 30 minutes. If the subject is uncomfortable during Octave System treatment, the treating investigator has the option to utilize additional measures to improve tolerability, including additional/different pain medication (e.g., see Section 10.5.1.2). If treatment remains intolerable after implementation of mitigation measures, the investigator or delegated study clinician must stop administering treatment, for the subject's safety, and the subject will be followed for AEs throughout the study's duration. In the case of an AE report, the subject will be followed until the subject's last study visit, until the AE is resolved or stabilized, the subject is lost to follow-up, or some other resolution of the event occurs.

Considering all risks and benefits of Ultherapy on the Octave System, the potential benefits to physicians and subjects seeking treatment outweigh the potential risks. The benefit/risk ratio of the device is considered acceptable when used on subjects seeking improvement of lines and wrinkles of the décolleté.

Additional information on device- and procedure-related contraindications, warnings, and precautions can be found in the current version of the Octave System IFU

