## 11.2.1.1 Standardized 2D Photographs

For assessment of the primary effectiveness endpoint, standardized 2D photographs will be taken at the screening visit and at Day 90, at a minimum. Among reconsented subjects, additional standardized 2D photographs will be taken at Day 180. A frontal view of the décolleté is to be obtained using the camera system provided, paired with the Canfield IntelliStudio platform to standardize image capture. Standardized 2D photographs will be utilized to complete the independent photographic review

Since photographs are of critical importance as a reference measure throughout the study, the 2D photographs taken at the screening visit (Visit 1) will be reviewed and accepted by the central photography vendor prior to treatment. If a subject's screening photographs are deemed unsatisfactory by the central photography vendor, photographs will be retaken at Visit 2. Any additional photographs collected at Visit 2 must be collected prior to treatment administration. If no repeat photography is needed, the screening photographs will default to the baseline (pre-treatment) photographs and will be used for reference throughout the study.

At each site, the respective study photographers must be trained in taking standardized photographs and follow the instructions provided in a separate photography user manual. It is of the utmost importance that subjects are photographed in highly standardized positions and with the same setup (i.e., standardized distance, area, views, color standard, lighting, and background). Every effort should be made to have the same trained study personnel take photographs at every visit, and to maintain the setup of the photo studio over the course of the study, with the identical and exact fixed camera positions for the different views and light setups.

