4.2 Intent-to-Treat (ITT) Population

The Intent-to-Treat (ITT) population consists of all subjects who are enrolled.

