6.1.1 Primary Effectiveness Endpoints

6.1.1.1 Primary analysis

The primary endpoint of the study is the proportion of treated subjects with improvement in lines and wrinkles of the décolleté by comparing photographs taken at Day 90 (post-treatment) with baseline (pre-treatment) photographs.

Each independent evaluator will assess “Improvement” or “No Improvement” between Photograph 1 (baseline) and Photograph 2 (post-baseline). Photograph 1 will be identified, and the independent evaluators will be blinded to the random distribution of treated versus untreated status of the comparator Photograph 2 (i.e., Day 90 post-treatment among treated subjects or post-baseline for untreated individuals). If photographs are declared as not assessable during the Day 90 assessment session, the evaluators will be instructed to rate the corresponding Photograph 2 as “No Improvement”.

Improvement will be declared if at least two blinded evaluators indicate “Improvement” for the comparator photograph. In case at least two evaluators declare a photograph as not assessable, the corresponding improvement score over all evaluators will be set to missing for the primary analysis.

The point estimate for the proportion of subjects fulfilling the primary endpoint will be described by frequency statistics for the ITT subset.

Effectiveness is established if:

- A. the point estimate is $\geq 65\%$ and
- B. the lower bound of the one-sided 95% Wilson CI is $> 50\%$.

Missing data, including a missing primary endpoint assessment in subjects with unacceptable or missing photographs at baseline or Day 90, will be imputed by multiple imputation. In case of complete data, no multiple imputation will be performed and the primary analysis is based on complete data for the ITT.

Imputation is done 50 times using a fully conditional specification logistic regression method, as implemented in SAS PROC MI with statement FCS LOGISTIC, and will use the investigational site and the baseline characteristics age and BMI as independent variables.

In a first step a total of $m=50$ imputed datasets will be generated, where missing data in the primary endpoint (improvement over all evaluators) is modelled via logistic regression based on input variables site, age and BMI at baseline. CCI

CCI

CCI

CCI response is coded as (0=no response (“no improvement”), 1=response (“improvement”)). The two-sided 90% Wilson CI ([WL, WU]) will be calculated using the following steps, as detailed in [1]:

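### The protocol contradicts itself on whether a subject stopped for pain has the Day 90 photograph, and a missing one would be imputed without regard to incomplete treatment

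*Protocol*

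**What the plan says.** **Follow-up after treatment is stopped**

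- Protocol 10.5.3, for pain that remains intolerable after the permitted medication: "treatment should be discontinued, and the subject will be followed for safety only".
- Protocol 9.2.6.1, for any discontinuation of treatment: "The investigator should request that a subject discontinuing treatment continue to participate in the study and complete all remaining visits and safety follow-up assessments".
- Protocol 9.2.6.2: "The only reasons a subject will not be followed for all scheduled visits include withdrawal of consent". The list goes on to continuous non-compliance and loss to follow-up, and the investigator may also discontinue a subject if medically necessary. Stopped treatment is not listed.
- Protocol 6.3, for treatment that remains intolerable: "the subject will be followed for AEs throughout the study's duration". It is silent on photographs.
- Protocol 11.2.1.1, for the primary endpoint: "standardized 2D photographs will be taken at the screening visit and at Day 90, at a minimum". No exemption is given for stopped treatment.

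**Analysis**

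- SAP 4.2: "The Intent-to-Treat (ITT) population consists of all subjects who are enrolled". A partly treated subject is therefore in the primary analysis set.
- SAP 6.1.1.1: a missing primary assessment, including one due to "missing photographs at baseline or Day 90, will be imputed by multiple imputation". The visible model uses site, age and baseline BMI.
- SAP 6.1.1.2 adds an ITT analysis that counts missing outcomes as no improvement, as a sensitivity analysis.

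**The concern.** The photograph is the only source of the primary endpoint, and the protocol files it under effectiveness assessments (11.2.1). An instruction to follow a subject for safety only can fairly be read as leaving it out, and 10.5.3 is the section specific to pain stops. Another site can just as fairly follow 9.2.6.1 and take it. Whether the outcome exists would then depend on which section a site applies.

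If the photograph is not taken, the value is missing because of how treatment went, and the imputation model cannot see that. The subjects with the least treatment would be given roughly the improvement rate of those with the most. The success rule leaves little room for this, because the 65% point-estimate condition sits only 5 points below the assumed rate of 70%.

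**Working it through.** **The plan's own figure.** Protocol 13.1 and SAP section 3 give at least 85% power with 80 evaluable subjects at a true rate of 70%. Success needs a point estimate of at least 65% and a one-sided 95% Wilson lower bound above 50%. At n = 80 both conditions are met from 52 responders (52/80 = 65.0%, lower bound 55.9%). The exact binomial probability of 52 or more at 70% is 86.3%, so the stated power reproduces. The Wilson condition alone needs only 48, so the 65% condition decides. With all 90 enrolled subjects observed, 59 responders are needed (65.6%), with probability 85.0%.

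**Inputs**

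- n = 90 enrolled (Protocol 13.1).
- p = 70% in subjects with a completed session (planning rate, Protocol 13.1).
- k = number stopped for pain without a photograph. Not in the documents; assumed 1 to 10. The upper end equals the whole attrition allowance.
- q = improvement rate after incomplete treatment. Not in the documents; assumed 70% (no loss of effect) down to 0%.

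**Bias.** Imputation from site, age and BMI has an expected value close to the observed rate p. The rate had all 90 been observed is ((90 − k)p + kq)/90. The difference is

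bias = k(p − q)/90.

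- k = 1, q = 0%: 1 × 0.70/90 = 0.8 points
- k = 5, q = 60%: 5 × 0.10/90 = 0.6 points
- k = 5, q = 30%: 5 × 0.40/90 = 2.2 points
- k = 10, q = 0%: 10 × 0.70/90 = 7.8 points
- any k, q = 70%: 0

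**Chance of success.** The imputed case is approximated by applying the rule to the 90 − k observed subjects. The photographed case sums the two exact binomials and needs 59 of 90.

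| k | q | Imputed | Photographed |
|---|---|---|---|
| 3 | 50% | 84.8% | 81.5% |
| 3 | 30% | 84.8% | 77.8% |
| 5 | 65% | 82.9% | 83.6% |
| 5 | 60% | 82.9% | 82.1% |
| 5 | 30% | 82.9% | 72.0% |
| 9 | 30% | 84.6% | 58.7% |

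A simulation of the multiple imputation with the SAP's interval formula (20,000 runs, 50 imputations, no covariates) gave 83.1% for k = 5, in line with the approximation. The slight reversal at k = 5, q = 65% arises because the whole-number threshold is 56/85 = 65.9% in one case and 59/90 = 65.6% in the other.

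**Where it could turn the result.** With five stopped, 56 of 85 photographed is the smallest passing count. If two or fewer of the five had improved, the full set would give at most 58/90 = 64.4% and fail. With three or more it would reach at least 59/90 and pass.

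**The case against.** A reader might infer that subjects stopped for pain have no Day 90 photograph and that the improvement rate is therefore inflated. The documents support neither as a fact. No section says the photograph is omitted, and 9.2.6.1, 9.2.6.2 and 11.2.1.1 all point towards its being taken. Section 6.3 asks for adverse-event follow-up without excluding anything else. The Schedule of Events, which might settle the matter, is not in the available text.

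Inflation further requires that some subjects are stopped and that they improve less often. Someone stopped near the end may have had most of the planned lines. Section 6.3 reports tolerable, transient discomfort in earlier studies of the first-generation system, and 10.5.3 stops treatment only after the permitted pain medication has been used up. Few stops and a small loss of effect are both possible, and the table shows that the effect on success is then negligible.

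The plan also has safeguards. The worst-case ITT analysis counts a missing subject as no improvement, the per-protocol set excludes incomplete sessions, and treatments stopped for pain are listed (SAP 6.2.1). A reader could find these subjects and recompute.

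All of this limits the size and certainty of the point. It does not remove the contradiction. The worst-case analysis mixes these subjects with every other missing outcome and does not decide success. The observed-case ITT and per-protocol analyses both leave out a pain-stopped subject who has no photograph.

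**Conclusion.** The point holds as an internal contradiction on collecting the primary outcome, together with an SAP that has no visible rule for incomplete treatment in the primary analysis. The upward bias is conditional. It is zero if these subjects are photographed, if none are stopped, or if they improve as often as the rest. Otherwise it is at most 0.8 points per stopped subject at p = 70%, and it reaches 7.8 points only at the extreme of ten stopped and none improving. The loss in the chance of success ranges from nothing to substantial, depending on two quantities the documents do not give. Confidence is moderate, because the Schedule of Events and part of the imputation model text are not visible.

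**What to change.** **Protocol.** Reconcile 10.5.3 with 9.2.6.1 on outcome collection only. State that every subject who received any Octave lines, including those stopped early, is asked to have the Day 90 photograph (and Day 180 if reconsented), and that the images go to the blinded read and are analysed as observed. A matching sentence in 6.3 would remove doubt. The pain-control and stopping rules are not touched.

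**SAP.** For a subject stopped early who still has no photograph, pre-specify handling that does not simply borrow the fully treated rate. One example is a separate sensitivity analysis that counts only these subjects as no improvement. Making that the primary rule is an estimand choice for the sponsor, not a correction. It sets q to 0%, and with five such subjects the chance of success falls to about 60%, against 72% if they were photographed and 30% improved.

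**Cost.** A few sentences, and one frontal photograph per affected subject. Protocol 11.1 already carries safety follow-up to Day 90. The downside is that the improvement rate and the chance of success may be lower than under imputation.
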